### 16.5.3. Reporting Standards for Pharmacokinetic Data

Pharmacokinetic Concentration Data	
Descriptive Summary Statistics, Graphical Displays and Listings	Refer to IDSL PK Display Standards. Refer to IDSL Statistical Principle 6.06.1. Note: BLQ concentration values will be imputed as per GUI_51487 for descriptive summary statistics only.
NONMEM/Pop PK	Pop-PK file (CSV and SAS format) for the POP-PK and POP-PKPD

File	analyses performed by the Clinical Pharmacology Modelling and Simulation function will be created according to the POP-PKPD Dataset Specification document.
Pharmacokinetic Parameter Data	
Descriptive Summary Statistics, Graphical Displays and Listings	Refer to IDSL PK Display Standards. Refer to IDSL Statistical Principle 6.06.1.

## 16.6. Appendix 6: Derived and Transformed Data

### 16.6.1. General

Multiple Measurements at One Analysis Time Point

 
If there are two results identified at a single visit the latter of the two measurements will be flagged and used in any derivation of summary statistics. All values will be presented on listings.
 
Subjects having both High and Low values for Normal Ranges at any post-baseline visits for safety parameters will be counted in both the High and Low categories of “Any visit post-baseline” row of related summary tables. This will also be applicable to relevant Potential Clinical Importance summary tables.
 

Study Day

 
Calculated as the number of days from the date of the first dose of study treatment:                             
 
Ref Date = Missing → Study Day = Missing
 
Ref Date < First Dose Date → Study Day = Ref Date – First Dose Date
 
Ref Date ≥ First Dose Date → Study Day = Ref Date – (First Dose Date) + 1
 
 
 

Total observed time, time on treatment, time off treatment, missing time

 
For subjects completing the Week 32 visit                             
 
Total observed time (days) = Week 32 visit date – Date of first dose + 1 day
 
Time on treatment (days) = Minimum(Week 32 visit date, Date of last dose + 28 days) – Date of first dose + 1 day
 
Time off treatment (days) = Week 32 visit date – Minimum(Week 32 visit date, Date of last dose + 28 days)
 
Missing time (days) = 0
 
 
 
For subjects not completing the Week 32 visit                             
 
Total observed time (days) = Study withdrawal date – Date of first dose + 1 day
 
Time on treatment (days) = Minimum(Study withdrawal date, Date of last dose + 28 days) - Date of first dose + 1 day
 
Time off treatment (days) = Study withdrawal date – Minimum(Study withdrawal date, Date of last dose + 28 days)
 
Missing time (days) = Predicted Week 32 visit date – Study withdrawal date, where predicted Week 32 visit date = Date of first dose + 224 days.
 
 
 

 

 

### 16.6.2. Change from Baseline Definitions

Definition	Reporting Details
Change from Baseline	= Post-Dose Visit Value – Baseline
% Change from Baseline	= 100 x [(Post-Dose Visit Value – Baseline) / Baseline]
Ratio to Baseline	= Visit Value / Baseline

**NOTES :**

- Unless otherwise specified, the baseline definitions specified in Section 5.2 will be used for derivations for endpoints / parameters.
- Unless otherwise stated, if baseline data is missing no derivation will be performed and result will be set to missing.

**16.6.3. Study Population**

Age

 
• GSK standard IDSL algorithms will be used for calculating age where birth day and month will be imputed 'PPD'
 
• Birth date will be presented in listings as 'YYYY'.
 
• Age will be calculated relative to the date of the screening visit (Visit 1).
 

Body Mass Index (BMI)
Calculated as Weight (kg) / [Height (m)]
Baseline HES Therapy

 
• Baseline oral corticosteroid use and baseline oral prednisone equivalent daily dose will be derived as detailed in Section 5.4.1.1.
 
• Cytotoxic therapy/immunosuppressive therapy and other HES therapy will be identified by clinical review of the concomitant medications page according to the following criteria:             
 
○ Medication type = "Hypereosinophilic syndrome"
 
○ Start date < Date of first dose of study treatment
 
○ Either "ongoing" or End date ≥ Date of first dose of study treatment
 
 
 
• Oral budesonide has negligible systemic exposure and will be counted as "Other HES therapy" rather than oral corticosteroid therapy.
 

Duration of HES

 
• Duration of HES in years will be calculated from the date of the screening visit (Visit 1) and the date of HES diagnosis as follows: Duration (years) = (Date of visit 1 – date of HES diagnosis)/365.25
 
• If the date of HES diagnosis is a partial date, a '01' will be used for a missing day and 'Jan' will be used for a missing month.
 

Exposure (therapeutic coverage)

 
• The number of days of exposure (therapeutic coverage) to study drug will be calculated based on the formula: Duration of exposure in days = Date of last dose of study treatment – date of first dose of study treatment + 29.
 
• Exposure in months will be calculated using the formula: Exposure (months) = (Exposure in days / 365.25) * 12
 
• Total subject years exposure will be calculated using the formula: Total subject-years exposure = (Sum across subjects of exposure in days)/365.25
 

### 16.6.4. Efficacy

HES Flare
Definition of HES Flare

 
• A HES flare is defined as either             
 
a) A HES-related clinical manifestation based on a physician-documented change in clinical signs or symptoms resulting in the need for either of the following:                 
 
- An increase in the maintenance OCS dose by at least 10mg/day for 5 days
 
- An increase in or addition of any cytotoxic and/or immunosuppressive HES therapy
 
 
 
or
 
b) Receipt of two or more courses of blinded active OCS during the treatment period.
 
 
 
• The maintenance OCS dose is the dose received during the 4 weeks prior to randomisation i.e. baseline OCS therapy, which should be maintained for the duration of the treatment period. If a subject has their OCS dose reduced during the treatment period, the maintenance dose will be redefined as the new dose they have received for at least 4 weeks. If the OCS dose is increased during the treatment period, the maintenance OCS dose will not be redefined and will remain as therapy taken during the 4 weeks prior to randomisation.
 
• Flares meeting endpoint definition a) will be captured on the 'flare details' form in the eCRF.
 
• An increase in blood eosinophils above the pre-defined threshold level (2 x baseline value or baseline value + 2500 cells/<math>\mu</math>L) without any other clinical manifestations during the study will lead to administration of blinded active OCS treatment (see Section 2.2). If a subject receives a second course of blinded active OCS during the 32-week treatment period, the subject will be considered to be experiencing a flare. The container list for the blinded OCS treatment (indicating which container numbers contained active OCS and which contained placebo OCS) will be used to define HES flares meeting endpoint definition b). This container list will be incorporated into the final SDTM data sets at the end of the study, at the same time as the randomised treatment information.
 

HES flare onset and resolution dates

 
• The onset and resolution dates of HES flares meeting endpoint definition a) will be recorded on the 'Flare details' form in the eCRF.
 
• The start date of HES flares meeting endpoint definition b) is defined as the date of the blood draw at which the second course of blinded active OCS was triggered via schedule blood sampling for eosinophil monitoring. The resolution date for a flare meeting endpoint definition b) is the date of the first blood draw at which blood eosinophil count is below the threshold to trigger blinded active OCS (see protocol Section 6.4 for full details of blood eosinophil monitoring).
 

HES flare during Week 20 through Week 32

 
• Defined as a HES flare starting or ongoing on or after the date of the Week 20 visit (Visit 8) up to and including the date of the Week 32 visit (Visit 11).
 

Time to First HES Flare

 
• Calculated for each subject as (Onset date of first HES flare – Date of first dose of study treatment) + 1
 

HES Flare
Rate of HES Flares

 
For subjects completing the study, the rate of HES flares will be calculated as <math display="block">\frac{365.25 \times \text{Number of observed HES flares}}{\text{Date of Week 32 (Visit 11)} - \text{Date of first dose of mepolizumab} + 1}</math> 
 
For subjects withdrawing prematurely from the study, the rate of HES flares will be calculated as <math display="block">\frac{365.25 \times \text{Number of observed HES flares}}{\text{Date of study withdrawal} - \text{Date of first dose of mepolizumab} + 1}</math> 
 
 
The number of HES flares is the number of unique starting dates for HES flares. To be considered as a separate episode of HES flare, the start date of a HES flare must be at least 14 days apart from the resolution date of the preceding HES flare.
 
 
For flares meeting endpoint definition b), each subsequent course of blinded active OCS beyond 14 days from the resolution date of the preceding flare will be considered as an additional flare (e.g., 3 courses of blinded active OCS are considered as 2 flares, 4 courses of blinded active OCS are considered as 3 flares, etc.).
 

Subjects who have an elevated blood eosinophil level (2 x baseline value or baseline value + 2500 cells/μL) during the 32-week study treatment period

 
Subjects with elevated blood eosinophils either 2 x baseline value or baseline value + 2500 cells/μL during the 32-week study treatment period will be identified from the central laboratory haematology results. Samples taken from the date of first dose of study medication up until the date of Visit 11 (Week 32) will be considered in the derivation. Baseline will be defined as in Section 5.2.
 

Worst Level of Fatigue in Past 24 Hours (BFI Item 3)

 
A BFI item 3 score for baseline and each week of treatment will be derived by taking the mean of up to 7 available daily assessments in each week of treatment.
 
Assessment windows defining each week will be based on the date recorded for each BFI assessment and are defined in Section 16.3.1.
 

HES Symptom Severity Based on HES Daily Symptoms (HES-DS)

 
For each of the 6 symptom domains (muscle/joint pain, chills or sweats, abdominal pain or bloating, breathing symptoms, nasal or sinus symptoms and skin symptoms, a symptom score for baseline and each week of treatment will be derived by taking the mean of up to 7 available daily assessments in each weekly assessment window.
 
Assessment windows defining each week will be based on the date recorded for each HES-DS assessment and are defined in Section 16.3.1.
 
A symptom score for most bothersome symptoms will be derived by taking the mean of the symptom scores for the up to 3 symptom domains identified by the subject as most bothersome at visit 2 (Week 0).
 

BFI Total Score

 
The BFI total score (range 0 – 10) will be calculated as the mean of the 9 domain scores (range 0 – 10) recorded for the weekly assessment. If less than 4 domain scores are complete, the BFI total score will be set to missing.
 

**16.6.5. Safety**

Adverse Events
Drug Related AEs
AEs with relationship marked 'YES' or relationship missing.
AEs Leading to Permanent Discontinuation from Study Treatment or Withdrawal from the Study
AEs with action marked "Study treatment withdrawn" or withdrawn from study status marked "YES", or a response to either of these questions is missing.
AEs on Day of Dosing
AEs with an onset date equal to a study treatment dosing date and an onset time on or after the study treatment dosing time.
AE Time Since First Dose

 
If AE onset time is missing, calculate in days as follows:-                             
 
If AE start date < Date of first dose of study treatment then Time since first dose = AE start date - Date of first dose of study treatment
 
If AE start date ≥ Date of first dose of study treatment then Time since first dose = AE start date – Date of first dose of study treatment +1
 
Missing if AE start date or date of first dose of study treatment is missing.
 
 
 
If AE onset time is present, calculate in days, hours, minutes as Time since first dose = AE start date/time – Date/time of first dose of study treatment
 

AE Duration (Days)

 
If AE onset time is missing, calculate in days as AE end date – AE start date + 1
 
If AE onset time is present, calculate in days, hours and minutes as AE end date/time – AE start date/time
 
Missing if AE start date or end date is missing.
 

AEs of Special Interest

 
See Section 11.1.1.
 

ECG

 
QTc(B) (msec) will be derived from QT (uncorrected in msec) and RR interval (msec) as
 
 $QTc(B) = \frac{QT}{\sqrt{\frac{RR}{1000}}}$

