7.4.1.1. Time period and Frequency for collecting AE and SAE information

- Any SAEs assessed as related to study participation (e.g., protocol-mandated procedures, invasive tests, or change in existing therapy) or related to a GSK product will be recorded from the time a subject consents to participate in the study up to and including any follow-up contact.
- AEs will be collected from the start of study treatment until the follow-up contact (see Section [7.4.1.3](#)), at the timepoints specified in the Time and Events Table (Section [7.1](#)).
- Medical occurrences that begin prior to the start of study treatment but after obtaining informed consent may be recorded on the Medical History/Current Medical Conditions section of the CRF.
- All SAEs will be recorded and reported to GSK within 24 hours, as indicated in Section [12.4.6](#).
- Investigators are not obligated to actively seek AEs or SAEs in former study subjects. However, if the investigator learns of any SAE, including a death, at any time after a subject has been discharged from the study, and he/she considers the event reasonably related to the study treatment or study participation, the investigator must promptly notify GSK.

NOTE: The method of recording, evaluating and assessing causality of AEs and SAEs plus procedures for completing and transmitting SAE reports to GSK are provided in Section [12.4.5](#).

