### 16.4.4. Treatment Phases for Adverse Events

Study Phase	Definition
Pre-Treatment	AE onset date/time < Date/time of first dose of study treatment
On-Treatment	Date/time of first dose of study treatment ≤ AE onset date/time ≤ Date of last dose of study treatment + 28 days
Post-Treatment	AE onset date > Date of last dose of study treatment + 28 days

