#### 16.7.2.1. Handling of Missing and Partial Dates

Element	Reporting Detail
General	
 
Partial dates will be displayed as captured in subject listing displays.
 

HES Flare and Adverse Events	
 
Any partial dates for HES flare and adverse events will be raised to data management. If the full date cannot be ascertained, the following assumptions will be made:
 

Element	Reporting Detail
	
 
○ If the partial date is a start date, a '01' will be used for the day and 'Jan' will be used for the month.
 
○ However, if this imputation results in a date prior to the first dose of study treatment and the event could possibly have occurred during treatment from the partial information, then the date of the first dose of study treatment will be assumed to be the start date.
 
○ The event will then be considered to start on-treatment (worst case).
 
○ If the partial date is a stop date, a '28/29/30/31' will be used for the day (dependent on the month and year) and 'Dec' will be used for the month.
 
● Completely missing start or end dates will remain missing, with no imputation applied. Consequently, time to onset and duration of such events will be missing.
 
● The recorded partial date will be displayed in listings.
 

Concomitant Medications	
 
● Partial dates for any concomitant medications recorded in the CRF will be imputed using the following convention:                             
 
○ If the partial date is a start date, a '01' will be used for the day and 'Jan' will be used for the month
 
○ If the partial date is a stop date, a '28/29/30/31' will be used for the day (dependent on the month and year) and 'Dec' will be used for the month.
 
 
 
● The recorded partial date will be displayed in listings.
 

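### The SAP's day-of-dosing AE rule has no branch for a missing onset time, so untimed dosing-day AEs fall out of Table 4.13 and Listing 34

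*SAP*

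**What the plan says.** SAP 16.6.5 (Safety) defines AEs on the day of dosing as "AEs with an onset date equal to a study treatment dosing date and an onset time on or after the study treatment dosing time". The definition feeds one summary (Table 4.13) and one listing (Listing 34).

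The next derivation in that section, time since first dose, begins "If AE onset time is missing, calculate in days as follows", and AE duration has a similar fallback to dates. Two further definitions there state what a blank means. Drug-related AEs are "AEs with relationship marked 'YES' or relationship missing". The definition of AEs leading to discontinuation or withdrawal ends "or a response to either of these questions is missing".

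SAP 16.7.2.1 covers incomplete dates: "Any partial dates for HES flare and adverse events will be raised to data management". If the full date cannot be found and the event could have started during treatment, it is assigned to the on-treatment phase, which the SAP labels the worst case. That section does not address a complete date with no time.

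SAP 16.4.4 sets the AE phase by comparing date/times. Pre-treatment, for example, is "AE onset date/time < Date/time of first dose of study treatment". It has no missing-time rule either. Protocol 7.4.1.1 states that "AEs will be collected from the start of study treatment until the follow-up contact", while SAEs related to study participation or to a sponsor product are recorded from consent.

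**The concern.** The day-of-dosing rule joins two conditions, and the second can be judged only when a time is present. An event dated on a dosing day with a blank onset time therefore fails, although it may well have followed the injection. The plan foresees blank onset times, so this is not a remote case, and other AE definitions count a blank as an event. Here a literal program does the opposite.

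At stake is the completeness of the display that gathers all AEs dated to a dosing day and starting at or after the injection, whether or not the investigator labelled them as reactions. A related, smaller gap is that 16.4.4 does not say which phase applies to an AE dated on the first-dose date with no time.

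**Working it through.** The plan states no figure on this point, so there is none to reproduce. The check applies the rule as written and then traces which displays depend on it.

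**1. Rule applied to four same-day records.** Dosing at 10:00, onset date equal to the dosing date:

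| Onset time | Rule as written | With onset time missing also counted |
|---|---|---|
| 09:00 | excluded | excluded |
| 10:00 | included | included |
| 11:00 | included | included |
| missing | excluded | included |

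Only the untimed record changes. An event timed before dosing stays out under both versions. The Time and Events Table footnotes require the date and time of each administration in the CRF, so the element likely to be missing is the AE onset time.

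**2. Size.** Let m be the share of true post-dose, same-day AEs with no onset time. The rule keeps 1 − m of them. The documents give no value for m. Assuming a range of 0 to 20%:

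- m = 0%: 100% kept
- m = 2%: 98% kept
- m = 5%: 95% kept
- m = 10%: 90% kept
- m = 20%: 80% kept

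These are shares of events, not changes in subject incidence. Each subject has up to 8 administrations, and a subject with another timed dosing-day AE is still counted in the overall incidence. If one subject is lost altogether, incidence moves by 1/40 = 2.5 percentage points with 40 per arm, or 1/60 = 1.7 points with 60 per arm.

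**3. Direction of the SAP's other missing-data rules for AEs.** Missing relationship counts as drug-related. A missing action or withdrawal answer counts as leading to discontinuation or withdrawal. An ambiguous partial start date counts as on-treatment. The last is the closest parallel because it concerns timing.

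**4. Displays that use the rule.** Table 4.13 and Listing 34 only. Systemic and local reactions are collected on targeted eCRF pages (SAP 11.1.1) and reported in Tables 4.27 to 4.36 and Listings 35 to 38, which are defined without reference to the day-of-dosing rule. Listing 29 contains all AEs. After the first-dose date, a missing time has no bearing on whether an event falls in the on-treatment window.

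**5. The first-dose date.** With no onset time, 16.6.5 computes time since first dose from dates. For an AE on the first-dose date, the start date minus the first-dose date is 0, and 0 + 1 = day 1, which is the value for an event on or after the first dose. This agrees with the worst-case direction in 16.7.2.1. Both point to on-treatment, but 16.4.4 does not say so.

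**The case against.** The strongest case against the point has four parts.

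- **The SAP does not tell anyone to drop these events.** It is silent, and a careful programmer might include them. AE analyses also follow sponsor data standards that are not in the documents, and the eCRF may force a time. This stands as a limit on size. It does not remove the gap, because the definition states a condition that an untimed event cannot meet.
- **The neighbouring rules for missing relationship and action concern attribution, not timing.** That is fair, but the partial-date rule does concern timing and also takes the worst case.
- **Counting untimed events costs specificity.** Blood is drawn before dosing, and at doses 2 to 8 an AE on the dosing date may precede the injection. This stands, and is the price of the change.
- **An untimed SAE on the first-dose date could truly be pre-dose.** Related SAEs are recorded from consent, and Table 4.23 summarises pre-treatment SAEs. This also stands. For SAEs an on-treatment assignment is a worst-case convention, not a deduction.

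A reader might infer two stronger claims. One is that acute reactions as a whole are under-counted. The documents do not support this, since those reactions are captured and tabulated separately. The other is that untimed first-dose-day events would sort as pre-treatment in SAS and leave every on-treatment and special-interest table. That rests on unseen code, and the SAP's own fallbacks, day 1 and worst case, point the other way.

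**Conclusion.** The point holds as a minor error of specification. Applied as written, the rule leaves an untimed dosing-day AE out of Table 4.13 and Listing 34, contrary to how the SAP treats missing AE information elsewhere. The effect stops at those two displays. No efficacy result is affected, and no conclusion on AEs of special interest has been shown to change.

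The number of events lost is unknown and may be zero. The 0 to 20% range above is an assumption that shows how the loss scales, not an estimate. It would be tempting to set a one-subject shift against the 8% and 3% local reaction rates in the Protocol 4.6.1 risk table. That comparison does not apply: those rates come from severe asthma studies and describe injection-site reactions, which this trial reports in Tables 4.35 and 4.36 without the day-of-dosing rule.

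The conclusion assumes that the definition is programmed literally and that some AE onset times are missing, as 16.6.5 anticipates.

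**What to change.** In SAP 16.6.5, add at the end of the day-of-dosing definition: or onset time missing. Footnote Table 4.13 and Listing 34 with the number of events included on that basis, so that readers can see how far the display depends on it.

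For consistency, add to SAP 16.4.4 that a non-serious AE dated on the first-dose date with no onset time is On-Treatment. Treat untimed SAEs on that date the same way as the worst case, with a footnote, since some could be pre-dose.

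The cost is two clauses and the footnotes, with no new data collection. A few untimed AEs that began before dosing may be counted as dosing-day events, and the footnote discloses the upper limit on that number. The change should be made before unblinding.
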